# 3.4.2 Patient adherence and acceptability

Patient adherence to the interventions will be monitored via attendance records kept by the therapists. In addition, participants receiving the CBA or PEP interventions will be contacted by telephone interview by member of trial office Aberdeen at time of session 4 (approximately week 8) and session 8 (approximately week 26). They will be asked to indicate on a scale from 0 (not at all) to 10 (completely), if they think that this treatment is the right approach and their willingness to engage and adhere to the intervention. At the same time, the therapists will be asked during supervision to what extent they think that the participant has engaged with treatment and adhered to the agreed actions and

plans. Intervention acceptance by participants will be evaluated in all three treatment arms using the Client Satisfaction Questionnaire [44] at 28 weeks.

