Patient adherence (attendance records)	SR			х	х	Х					
Patient engagement and adherence (telephone call)	Q	3			х	Х					
Patent engagement and adherence (therapist view)	Q	2			х	Х					
Patient acceptability (Client Satisfaction Questionnaire)	Q	8				~					
Qualitative process evaluation											
Qualitative evaluation in participants (5% sample)	I										
Qualitative evaluation in therapists (all)	I										
Economic evaluation											
Health care costs from participants per diaries	D			✓	✓	√	✓				
Additional (personal) costs for participant per diaries	D			✓	✓	√	✓				
Cost associated with delivery of therapy	SR			✓	✓	√	✓				
Health related quality of life using SF-12 for calculation of QALY				✓	✓	√	✓				
Changes in well-being data using ICECAP	Q	5		✓	✓	√	✓				
Changes in life satisfaction	Q	1		~	✓	~	✓				
Optional blood sample for future ethically approved researc	 h										
1 x PAXgene RNA				✓	✓	√					
1 x PAXgene DNA				✓							
1 x serum				✓	✓	√					

**Key: B**, blood sample taken specifically for LIFT; **CRF**, part of case report form completed by research nurse during visit; **D**, separate diary for participant to keep; **I**, interviews performed after the last follow-up visit; **MR**, information extracted from medical record; **Q**, data derived from questionnaire; **S**, information obtained during pre-study invite; **SC**, Scanner; **SR**, information extracted from LIFT study records and logs; **T**, test done specifically for LIFT; **x**, outcome collection at same time frame but separate from assessment visit

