Our planned primary Intention-to-Treat analyses (ITT) will compare PEP + usual care versus usual care alone, and CBA + usual care versus usual care alone. This was based on a standardised effect size of 0.50 (considered credible in other pragmatic effectiveness studies), which would equate to being powered to detect a minimal important clinical difference of 2 units in the CF Scale, assuming a common standard deviation across the randomised groups of 4 units, as with PACE ¹⁹. Assuming an overall significance level of 5% (by calculating the two pre-specified randomised groups comparisons, PEP + usual care vs. usual care alone and CBA + usual care vs usual care alone, at 2.5%, to maintain an overall level of not more than 5%) and a power of 90%, we require 100 evaluable participants in each of the three groups.

11 Statistical Methods

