11.2 Statistical Analysis

LIFT has repeated measures on individual participants nested within site suggesting a multilevel model with an appropriate link function depending on the outcome. The analysis will adjust for the outcome variable at baseline as a covariate (when available) as well as the design factors also at baseline [diagnosis (RA, SLE, AxSpA or other IRD), the presence/absence of depressive symptoms HADS depression subscale >10)]. Centre clustering will be accounted for using a random effects robust variance.

11.2.1 Primary Outcome - Effectiveness Analysis.

We will test the primary hypothesis for between-group change in the primary outcome for each of the two pre-specified comparisons (CBA + usual care vs usual care alone and PEP + usual care vs usual care alone) using treatment and its interaction with time fitted as fixed effects, and we apply standard regression diagnostics. The main analysis will focus on the 56 weeks after baseline – providing effect sizes for each of the active arms compared to usual care. Standard regression diagnostics will be applied.

A Complier Average Causal Effect (CACE) analysis will be considered as a sensitivity analysis. Patent engagement & adherence (therapist view) at 8 weeks forms the CACE variable (if missing the 4 weeks reported value will be substituted) as a continuous instrumental variable in the CACE analysis

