Recommend this program to a friend? 1:No, definitely not; 2:No, I don't think so;		
3:Yes, I think so; 4:Yes, definitely; 99:Not answered;		
Satisfied with the amount of help received? 1:Quite dissatisfied; 2:Indifferent or mildly dissatisfied; 3:Mostly satisfied; 4:Very satisfied; 00:Net answered;		
 Have the services received helped to deal more effectively with problems? 1:Yes, they helped a great deal; 2:Yes, they helped; 3:No, they really didn't help; 4:No, they seemed to make things worse; 99:Not answered; 		
How satisfied with the service received overall? 1:Very satisfied; 2:Mostly satisfied; 3:Indifferent or mildly dissatisfied; 4:Quite dissatisfied; 99:Not answered;		
Would you come back to this program if needed? 1:No, definitely not; 2:No, I don't think so; 3:Yes, I think so; 4:Yes, definitely; 99:Not answered:		

*Continuous data n; mean (sd), median (IQR) and (min, max)

‡ Summary of Item 1-8 plus overall Score. Also Item 9 indicates causality, BUT will need to be coded and analysed separately (text data) SG : TBC by [name]

† Patent engagement & adherence (therapist view) at 8 weeks forms the CACE variable (if missing the 4 week) reported value to be substituted

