13.4 Primary outcome summaries and model Estimates

Table 8: Primary outcome for Fatigue: Summaries*# and Model results

	CBA N =	PEP N=	Usual Care N =	Effect sizeª	95% CI	p- value	Effect size ^b	95% CI	p- value
Chalder Fatigue	Scale (Con	bined Liker	t score) 0-33 *c						
Baseline									
10wks									
28wks									
56wks (p)									
Fatigue Severity	/ Scale (FSS) *c							
Baseline									
10wks									
28wks									
56wks (^p)									
Baseline									
10wks									
28wks									
56wks (p)									

All models adjusted for their baseline outcome measure, HADS depression subscale >10 at baseline as fixed effects fixed effect with Centre clustering and individuals nested within centres as random effects *Continuous data:n; mean (sd), median (IQR) and (min, max)

Binary x/n (%)

^aMean difference between CBA and Usual care

^b Mean difference between PEP and Usual care

P Primary time point

^cMultilevel mixed-effects generalized linear model (glm) accounting for different time points.

Recall:

- The primary intention to treat analyses will compare PEP + usual care versus usual care alone, and CBA + usual care versus usual care giving effect sizes ^a and ^b
- The main estimate of treatment effect will focus on the 56 weeks after baseline.

- If the effect of intervention is positive on the CF, then the FSS outcome will be formally analysed. Should the intervention have no effect on the CF, then an explorative analysis of the FSS outcome will be performed.
- All analyses and reporting will follow the guidelines of the CONSORT statement developed specifically for social and psychological intervention trials ³
- CACE analysis as a sensitivity analysis will be considered for the primary outcome Chalder Fatigue

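### The SAP names the therapist's engagement rating, not randomised allocation, as the CACE instrument, gives usual care no value, and labels the rating times in a way that fails as a pair

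*SAP*

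**What the plan says.** SAP 11.2.1 says that a CACE analysis will be considered as a sensitivity analysis. Its variable is the therapist's view of engagement and adherence at 8 weeks, with a fallback: "if missing the 4 weeks reported value will be substituted". That variable enters "as a continuous instrumental variable in the CACE analysis". The footnote to SAP Table 5 repeats the rule: "Patent engagement & adherence (therapist view) at 8 weeks forms the CACE variable". SAP 13.4 fixes the outcome and the status: "CACE analysis as a sensitivity analysis will be considered for the primary outcome Chalder Fatigue".

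Protocol 3.4.2 says when the ratings are made. Participants receiving CBA or PEP are telephoned "at time of session 4 (approximately week 8) and session 8 (approximately week 26"; for the therapist rating it adds: "At the same time, the therapists will be asked during supervision to what extent they think that the participant has engaged". The SAP appendix (section 15) also lists the therapist rating by session, at sessions 4 and 8. It describes the rating as one item and leaves absent values missing. The matrix in Protocol 3.8 lists two therapist items, marked with an x under weeks 10 and 28.

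**The concern.** A CACE estimate keeps the protection of randomisation because allocation is the instrument and treatment received is the exposure. The SAP gives the instrument's role to a rating made during treatment. Such a rating can share causes with fatigue at 56 weeks: patients who would have improved anyway may engage more, or the most unwell may be the most motivated.

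Usual-care participants have no therapist and so no rating, and no value is assigned to them. An analyst must therefore invent a coding or has no comparison to make.

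The week labels add a second ambiguity: two statisticians could use different ratings as the exposure. At stake is whether this sensitivity analysis of the primary outcome can be reproduced and interpreted next to the ITT result.

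**Working it through.** **Plan figures.** The plan gives no figure for the CACE analysis. The SD of 4 CF units and 100 per group used below come from SAP section 10, which plans each comparison "at 2.5%, to maintain an overall level of not more than 5"%. Those figures reproduce: 2 × (2.2414 + 1.2816)² / 0.5² = 99.3, so 100 per group.

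**Instrument and usual-care value.** Let Z be allocation, E the rating and Y the CF score at 56 weeks, for one active arm against usual care.

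- *Usual care left blank.* Everyone with a rating has Z = 1. Z is then constant, and no contrast with usual care can be estimated, whichever of Z and E is called the instrument. Correcting the word for the instrument alone is not enough.
- *Usual care set to 0, E as instrument for Z, no true effect.* Scale E to mean 1 in the active arm, with coefficient of variation CV. With equal arms, Cov(E, Z) = 0.5 − 0.5 × 0.5 = 0.25 and Cov(E, Y) = 0.5 × r × CV × SDres, where r is the correlation of rating with outcome given baseline CF. The estimate tends to 2 × r × CV × SDres instead of 0.
- *Usual care set to 0, E as its own instrument.* This is ordinary regression on the rating. Var(E) = 0.25 + 0.5 × CV², and the estimate tends to 0.5 × r × CV × SDres / Var(E).
- *Usual care set to 0, Z as instrument, E as exposure.* Cov(Z, Y) = 0 under no effect, so the estimate is centred on 0 whatever r is.

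**Illustration only.** Assume a baseline correlation of 0.5, so SDres = 4 × √(1 − 0.5²) = 3.46, and CV = 0.4. None of CV, r, the baseline correlation or the zero coding is in the documents.

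- E as instrument for Z: |r| = 0.1, 0.2, 0.3 gives 2 × |r| × 0.4 × 3.46 = 0.28, 0.55, 0.83 CF units.
- E as its own instrument: Var(E) = 0.25 + 0.08 = 0.33, giving 0.21, 0.42, 0.63 units at mean engagement.
- Sign: negative r (better prognosis, more engagement) gives a spurious benefit; positive r gives spurious harm or hides a benefit. With r = 0 there is no bias.
- Simulation of 10,000 null trials for negative r agrees (0.28, 0.56, 0.83 for the first case). With allocation as instrument, estimates were within 0.01 of 0 and the false-positive rate was 2.5% to 2.6% at the 2.5% level.

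**Timing.** The course is seven sessions (Protocol 4.3.2), so the booster is session 8. It falls 22 weeks after the start of therapy, and therapy starts on average 4 weeks after baseline (Protocol 4.1): 22 + 4 = 26, matching Protocol 3.4.2. The matrix columns at weeks 10 and 28 do not conflict with this, since x means "outcome collection at same time frame but separate from assessment visit".

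- *Labels read as weeks.* The 8-week rating is session 4, but no rating is scheduled around week 4, which on the randomisation clock is the average start of therapy. The fallback does not exist.
- *Labels read as sessions (8, else 4).* Both ratings exist and match the SAP appendix, but the word weeks is wrong and the exposure is a different, later rating.

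On the protocol's approximate weeks the two ratings are 26 − 8 = 18 weeks apart. That gap is not firm. SAP 2.3 gives a 14-week course; seven sessions spread evenly put session 4 about 6 to 8 weeks after the start, so the gap could be 22 − 8 = 14 to 22 − 6 = 16 weeks.

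**The case against.** The strongest reply is that this is wording. The SAP first calls the rating the CACE variable and then calls it continuous, which suits a compliance measure inside an instrumental-variable analysis. The protocol's mediation section (10.2) shows that the team knows randomisation-based instruments. This stands as a likely explanation, and a reader should not infer that a confounded analysis is deliberately planned. It does not repair the text, because allocation is never named as the CACE instrument and the mediation passage does not cover CACE.

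The appendix rule that absent ratings stay missing might seem to settle usual care. It does not clearly do so: for people with no sessions the rating is not applicable rather than missing. The sound statement is that the SAP is silent.

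On timing, the 8-week label alone fits session 4, so it is too strong to say that both labels are wrong. They fail only together, and a slip of weeks for sessions is the likelier explanation.

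A reader might infer from the illustration that a CACE benefit alongside a null ITT result is to be expected. The numbers do not support that. With no true effect and the rating as instrument for allocation, that pattern occurred in 1.1%, 2.7%, 8.6% and 19.1% of simulated trials for r = 0, −0.1, −0.2 and −0.3. The sign of r is also unknown.

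Finally, SAP 11.4 defers post-randomisation adherence analyses to a secondary phase, and CACE is only to be considered. That lowers the stakes, but this is the SAP's only CACE specification.

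**Conclusion.** The point holds as a specification defect in a sensitivity analysis. As written, the contrast with usual care is either not estimable or not protected by randomisation, and biased in either direction if engagement is related to prognosis. The size cannot be derived from the documents. The 0.28 to 0.83 CF units, against a target difference of 2, rest on an assumed CV, correlation and usual-care coding; they show a mechanism and do not measure this SAP.

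The two rating labels cannot both be right as weeks, and the two readings select different ratings. The number of therapist items differs between protocol matrix and SAP appendix, and the item used is not named.

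It would be wrong to read this as a threat to the main result: the primary ITT analysis, sample size and error control do not depend on it. The change should be made, but the trial's conclusions do not hang on it.

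**What to change.** Amend SAP 11.2.1 and the footnote to Table 5:

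1. For each active arm against usual care, state that randomised allocation is the instrument and the therapist rating is the exposure.
2. State the therapist rating scale and set usual care to its no-engagement value. The 0 to 10 scale in Protocol 3.4.2 is described for the participant's telephone questions.
3. Replace the week labels with session numbers, saying which session is used and which is the fallback.
4. Reconcile two items (Protocol 3.8) with one (SAP appendix) and name the item used.

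Naming the estimator and covariates would help but is optional. The cost is SAP wording only: the ratings are already scheduled, and no new data are needed.

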11.2.2 Secondary outcome Analysis

The secondary outcomes will be analysed using analogous methods to also test for betweengroup change for each the secondary outcome for the two interventions compared to usual care using treatment, time and treatment/time interaction fitted as fixed effects.

11.3 Mediation and Moderator analyses: (These analyses will be a secondary phase)

If the effectiveness analysis shows significant between group differences on the measures considered as putative mediators (i.e. significant ITT effects when these measures are considered as outcomes), then we will test for mediation of the effect of interventions on primary outcome(s) at 56 weeks through these putative mediators. The analysis will use causal mediation analysis based on parametric regression models (Landau et al, 2013).

This involves estimating a linear model for the mediator with group assignment, baseline CFS (or FSS), baseline mediator, diagnosis and presence/absence of depressive symptoms as covariates, and separately estimating a linear model for CFS (FSS) with the mediator, group assignment, baseline CFS, baseline mediator, diagnosis and presence/absence of depressive symptoms as covariates. The effect of group assignment on the mediator is multiplied by the effect of mediator on CFS (FSS) to estimate the indirect effect, and the effect of interventions on CFS (FSS) in the model including mediator is an estimate of the residual direct effect. The

indirect and direct effects sum to the total effect, and bootstrapping with 1000 replications will be used to obtain valid standard errors for the causal mediation effects. The proportion mediated is the indirect effect divided by the total effect. We will test for moderation of the mediation pathways by primary diagnosis.

Exploratory moderation analyses examined whether the between-group effect on CFS (FSS) was moderated by the following baseline variables: XX. The primary analysis models will be extended by including the moderator, its interaction with group assignment and a three-way interaction with group assignment and time as fixed effects. The difference in between-group effects at each level of the moderator will be calculated using the -margins- command in Stata.

The Moderation and Mediation analyses will be in place of any Subgroup analyses and is planned as a secondary analysis paper.

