*Mediation analysis:* We will use modern causal inference methods to investigate the set of mediator measures. If the effectiveness analysis shows significant between group differences in the mediators then we will use parametric regression models to test for effect of mediator on outcome, and the residual direct effect of treatment on outcome. Since all the measures are continuous, the indirect effects are calculated by multiplying relevant pathways and bootstrapping is used to produce valid standard errors for the indirect effects. All analyses will adjust for baseline measures of the mediators, outcome and putative measured confounders, and be tested for moderation by diagnosis. Mediation analyses are potentially biased by measurement error in mediators and hidden confounding between mediators and outcomes; we will build on our previous methodological and applied work in this context to include repeated measurement of mediators and outcomes to account for classical measurement error and baseline confounding. We will investigate the sensitivity of the estimates to these problems and that of unmeasured confounding using instrumental variable (IV) methods with baseline covariate by randomisation interactions as potential instruments.

*Moderation analysis:* We will examine differential treatment effects using the set of moderator measures by extending the intention to treat analysis models to include an interaction term between treatment and each of the moderators separately. We will use bias correction/cross-validation methods to identify robust evidence for individual moderation and for a moderation index, both on the overall effect and also along the steps of the mediation pathway.

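### SAP 11.3 leaves baseline FSS out of the mediation outcome model when FSS is the outcome: probably a drafting omission, but it conflicts with Protocol 10.2 and can confound the mediator-to-FSS path

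*SAP*

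**What the plan says.** SAP 11.3 sets out two regressions. The mediator model is described as "estimating a linear model for the mediator with group assignment, baseline CFS (or FSS), baseline mediator", so its fatigue baseline can follow the outcome being analysed. The outcome model is described as "separately estimating a linear model for CFS (FSS) with the mediator, group assignment, baseline CFS, baseline mediator". The outcome may be either scale, but the only fatigue baseline listed is CFS. Both lists then add diagnosis and depressive symptoms. (I read CFS as the Chalder Fatigue Scale, which the SAP elsewhere abbreviates CF.)

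The estimator is a product of coefficients: "The effect of group assignment on the mediator is multiplied by the effect of mediator on CFS (FSS) to estimate the indirect effect". The section then states that the "indirect and direct effects sum to the total effect, and bootstrapping with 1000 replications" will supply the standard errors, and it defines the proportion mediated as indirect over total.

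Three other places address the baseline covariate. Protocol 10.2, on mediation, says: "All analyses will adjust for baseline measures of the mediators, outcome and putative measured confounders". SAP 11.2, the general rule, says: "The analysis will adjust for the outcome variable at baseline as a covariate (when available". The footnote to SAP Table 8, which covers both Chalder Fatigue and FSS, says: "All models adjusted for their baseline outcome measure, HADS depression subscale >10 at baseline".

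**The concern.** A programmer working from SAP 11.3 would fit 56-week FSS on the mediator with baseline Chalder Fatigue but without baseline FSS. The two scales are not interchangeable: SAP 6.1 describes one as covering physical and mental symptoms and the other as covering the impact of fatigue. If baseline FSS drives both the later mediator and the later FSS, part of that shared baseline is credited to the mediator. Because mediation is tested only for measures that show a significant group difference, the group-to-mediator effect is non-zero by selection, and any error in the mediator-to-FSS coefficient carries into the product. Bootstrapping gives standard errors; it does not remove such an error. The stake is the reading of which measures carry the effect on FSS, which serves the protocol's secondary objective on mediators.

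**Working it through.** **The plan's own figure.** The documents give no number for the mediation analysis. The design figure does reproduce: 2 × (2.2414 + 1.2816)² × (4/2)² = 99.3, so 100 per arm, with power 0.902 at 100; 100/0.8 = 125, and 3 × 125 = 375. It is used below only to set the sample size for step 2.

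**Step 1. The lists side by side, with FSS as outcome.**

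| Source | Fatigue baseline |
|---|---|
| SAP 11.3, mediator model | CFS or FSS |
| SAP 11.3, outcome model | CFS only |
| Protocol 10.2, mediation | baseline of the outcome |
| SAP 11.2, general rule | baseline of the outcome |
| SAP Table 8 footnote | baseline of the outcome |

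With Chalder Fatigue as outcome, both models carry baseline CFS and there is no conflict. With FSS as outcome, using baseline FSS in the mediator model makes the two lists differ. Using baseline CFS in both makes them match, but still leaves FSS without its own baseline.

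**Step 2. The decomposition.** Write T for group, C0 and F0 for baseline CFS and FSS, and M0 for the baseline mediator. Let a be the group-to-mediator coefficient, b the mediator-to-FSS coefficient and d the direct effect. With one covariate set and one set of records, least squares gives a × b + d = total exactly. With F0 in the mediator model and C0 in the outcome model,

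a(F0) × b(C0) + d(C0) = total(C0) + [a(F0) − a(C0)] × b(C0),

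which is not the FSS-adjusted total. In 500 simulated samples of 200 records (two arms of about 100; CFS–FSS correlation 0.6; F0-to-mediator effect 0.2; other inputs as in step 3), the sum departed from the FSS-adjusted total with mean 0.001 and SD 0.056. It departed from the CFS-adjusted total with SD 0.010. With matched covariates the gap was zero to rounding. In large samples randomisation removes the gap: both were 0.32.

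**Step 3. Confounding of b.** All inputs are assumptions, since the documents give no correlations. Baselines are standardised; corr(C0, F0) is 0.5 to 0.8; each correlates 0.4 with M0; a = 0.4; b = 0.3; d = 0.2; M0-to-mediator effect 0.5; F0-to-FSS effect f = 0.5; residual SD 0.75 in each equation. The F0-to-mediator effect g runs over 0, 0.1, 0.2 and 0.3. Diagnosis and depressive symptoms are left out.

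Let v = Var(F0 given C0 and M0). Omitting F0 from the outcome model shifts b by

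f × g × v / (g² × v + 0.75²).

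The shift is zero if f = 0 or g = 0, and it does not depend on the true b.

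Worked case, correlation 0.5 and g = 0.3: the regression weights of F0 on C0 and M0 are (0.5 − 0.16)/0.84 = 0.405 and (0.4 − 0.20)/0.84 = 0.238. So v = 1 − (0.5 × 0.405 + 0.4 × 0.238) = 0.702. The shift is 0.5 × 0.3 × 0.702 / (0.09 × 0.702 + 0.5625) = 0.105/0.626 = 0.168. Hence b becomes 0.468, the indirect effect rises by 0.4 × 0.168 = 0.067, and the direct effect falls from 0.200 to 0.133.

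Simulation with 1,000,000 records per setting agrees. The true indirect effect is 0.4 × 0.3 = 0.120.

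| g | Indirect, correlation 0.5 | Indirect, correlation 0.8 | Excess over 0.120 |
|---|---|---|---|
| 0 | 0.120 | 0.120 | 0 |
| 0.1 | 0.145 | 0.133 | 0.013 to 0.025 |
| 0.2 | 0.168 | 0.145 | 0.025 to 0.048 |
| 0.3 | 0.187 | 0.156 | 0.036 to 0.067 |

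With F0 in the outcome model the estimate is 0.120 throughout. A separate simulation set the true mediator effect to zero, with group-to-mediator effect 0.4 in size, baseline mediator–FSS correlation 0.4, CFS–FSS correlation 0.5 to 0.8, FSS carry-over 0.4 to 0.6 and g from 0.1 to 0.3. It gave a spurious indirect effect of 0.008 to 0.068 in size, against at most 0.002 with baseline FSS. Its lower end is above zero only because g = 0 was not in the grid.

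**The case against.** The strongest reply is that nobody intended this. The mediator model in the same sentence names the FSS alternative, and three other places require the outcome's own baseline. The section is also visibly unfinished: its moderator list is a placeholder, and its results table and method reference are still to be confirmed. A reader might infer that the SAP deliberately chose baseline Chalder Fatigue as the adjustment for FSS. The documents do not support that, and I treat it as an omission. What remains is that SAP 11.3 gives its own complete covariate list and nothing later corrects it.

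A reader might also infer that the FSS indirect effect will be biased, or that the direct effect will be understated. Neither follows. Both links from baseline FSS must exist after adjustment for the baseline mediator and baseline CFS, baseline CFS removes part of the confounding, and the direction depends on the signs. Expressing the bias as a percentage of a 0.50 SD effect is unsupported too, because the plan states that effect for Chalder Fatigue and gives none for FSS.

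On the decomposition, the SAP names no separate total-effect model, so its sentence can be read as defining the total as the sum. That is fair. But the sum would then sit near a CFS-adjusted total for FSS, unlike the effectiveness analysis of FSS.

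Finally, Protocol 10.2 plans repeated measurement and instrumental-variable sensitivity analyses. These help with measurement error and unmeasured confounding, but they are no reason to leave out a measured baseline.

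**Conclusion.** The inconsistency is real and should be corrected. As written, the FSS mediation outcome model lacks baseline FSS, contrary to Protocol 10.2 and to the own-baseline rule elsewhere in the SAP. If it were coded that way, indirect plus direct could miss the FSS-adjusted total (SD about 0.056 at 100 per arm under the step 2 assumptions). The indirect effect could carry a spurious component of zero to about 0.07, in units of the baseline SD. Both sizes rest wholly on assumed correlations and path strengths.

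The reach is narrow: FSS mediation in a secondary-phase analysis. It would be wrong to infer that the trial's main results are at risk. Chalder Fatigue mediation, the randomised group-to-mediator path, the total effect and the primary effectiveness analysis are unaffected.

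**What to change.** In the SAP 11.3 outcome model, let the fatigue baseline read: baseline CFS (or FSS, matching the outcome). Add a sentence that, for each outcome, the mediator and outcome models use the same covariates and the same analysis sample. The cost is a phrase and a sentence in the SAP and one covariate in the code. FSS at week 0 is already in the assessment schedule, so no new data are needed. Making the change before the mediation models are fitted also avoids an undocumented choice between two versions later.

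### SAP 11.3 narrows the protocol's mediation plan, leaving out its measurement-error handling and unmeasured-confounding sensitivity analysis, yet still labels the indirect effects causal

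*SAP*

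**What the plan says.** Protocol 10.2 (mediation paragraph) names the weakness: "Mediation analyses are potentially biased by measurement error in mediators and hidden confounding between mediators and outcomes". It then commits to three safeguards:

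- Covariates: "All analyses will adjust for baseline measures of the mediators, outcome and putative measured confounders". The confounders are not listed.
- Measurement error: the analysis will "include repeated measurement of mediators and outcomes to account for classical measurement error and baseline confounding".
- Sensitivity: estimates will be checked against "unmeasured confounding using instrumental variable (IV) methods with baseline covariate by randomisation interactions as potential instruments".

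SAP 11.3 sets out two steps. The first is "estimating a linear model for the mediator with group assignment, baseline CFS (or FSS), baseline mediator, diagnosis and presence/absence of depressive symptoms as covariates". The second is a model for fatigue with "mediator, group assignment, baseline CFS, baseline mediator, diagnosis and presence/absence of depressive symptoms as covariates". The two coefficients are multiplied to give the indirect effect, standard errors come from 1000 bootstrap replications, the results are described as causal, and a proportion mediated is reported.

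Of the protocol's plan, SAP 11.3 keeps the baseline mediator and outcome and the test of moderation by diagnosis. It mentions no measurement-error model, no instrumental-variable or other sensitivity analysis for mediator-outcome confounding, and no follow-up time point for the mediator. The second model lists baseline CFS only, even when FSS is the outcome.

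**The concern.** Randomisation protects the path from arm to mediator. It does not protect the path from mediator to fatigue, because anything that drives both after allocation, or that the baseline values capture incompletely, enters the mediator coefficient. Apart from the baseline mediator, the SAP's covariates are the same ones used in its primary model (baseline outcome and the two minimisation factors), so nothing else was added for mediator-outcome confounding. Pain, sleep, anxiety, self-reported disease activity and CRP/ESR are all collected, plausibly affect both sides, and are left out.

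Bootstrap intervals describe sampling error and reveal neither confounding bias nor attenuation. Mediators are a secondary objective (Protocol 2.2) meant to guide later interventions, so a false or understated indirect effect could point that work at the wrong target.

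**Working it through.** **Scale.** The documents give no figure for the mediation analysis. Their sample size fixes the scale and reproduces. With a difference of 2, SD 4, two-sided 2.5% and 90% power (Protocol 10.1, SAP 10), n = 2 × (2.241 + 1.282)² × (4/2)² = 2 × 12.41 × 4 = 99.3, so 100 per arm. That figure is not in dispute.

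**Estimator.** Let a be the arm effect on the mediator, b the mediator coefficient in the fatigue model, and τ the total effect. The indirect effect is ab and the proportion mediated is ab/τ. Set the true b to zero and assume the arm moves mediator and fatigue by 0.5 SD each. Then a = τ in SD units, and the false proportion equals the false b. Every correlation, reliability and confounder effect below is an assumption. Diagnosis and depression are not modelled.

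**Three kinds of omitted confounder**, each with effect c (in SD) on both mediator and fatigue, and baseline-to-follow-up correlation or slope r:

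- A: acts only after baseline. With r = 0.6 the mediator's residual variance is 1 − 0.36 = 0.64. Then b = c²/0.64 if the confounder is part of that variance, or c²/(0.64 + c²) if it adds to it.
- B: shapes baseline and keeps acting. Follow-up = 0.6 × baseline + c × trait + noise of variance 0.64, and baseline = c × trait + noise of variance 1. Then b = c²/(0.64 + 2.28c²).
- C: stable trait loading equally on both measures at both times. With s = c², b = s(1 − r)/(1 + r − 2s²).

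| c | A, part of / added to variance | B | C, r = 0.5 | C, r = 0.6 | C, r = 0.7 |
|---|---|---|---|---|---|
| 0.2 | 6% / 6% | 5% | 1.3% | 1.0% | 0.7% |
| 0.3 | 14% / 12% | 11% | 3.0% | 2.3% | 1.6% |
| 0.4 | 25% / 20% | 16% | 5.5% | 4.1% | 2.9% |
| 0.5 | 39% / 28% | 21% | 9.1% | 6.8% | 4.8% |

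Example for C with c = 0.5 and r = 0.6: 0.25 × 0.4/(1.6 − 0.125) = 0.1/1.475 = 6.8%.

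**At the trial's size.** The two SAP models were simulated with 100 per arm, fatigue SD 4, total effect −2, arm effect on the mediator −0.5 SD, r = 0.5, true b zero, and 3000 trials per setting. Significance meant both paths significant at two-sided 5%, in place of the bootstrap. Let ρ be the correlation between the parts of mediator and fatigue that are not carried over from baseline (half the variance of each). Then b = 4 × 0.5ρ/(1 − 0.25), and the indirect effect is −0.5b.

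| ρ | Indirect effect (CF units) | Proportion | Declared significant |
|---|---|---|---|
| 0 | 0 | 0% | 5% |
| 0.1 | −0.13 | 7% | 16% |
| 0.2 | −0.27 | 13% | 46% |
| 0.3 | −0.40 | 20% | 80% |
| 0.5 | −0.67 | 34% | 98% |

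Adjusting for the shared cause, measured without error, returned the ρ = 0.3 case to about 0 and 5%. A stable cause explaining 10% or 30% of variance left −0.07 or −0.22 units (3% or 11% of the effect), significant in 8% or 35% of trials.

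**Measurement error.** With reliability R at both times, observed b/true b = (1/R − r²)/(1/R² − r²). For r = 0.5, R = 0.8 gives 1.00/1.3125 = 0.76, and R = 0.6 gives 1.4167/2.5278 = 0.56. A true indirect effect of −1.0 is then reported as −0.76 or −0.56.

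**The case against.** The case for leaving SAP 11.3 alone has substance. The protocol never names its measured confounders, so the SAP's baseline adjustments can be read as one way of filling an open phrase. Adjusting for baseline mediator and baseline fatigue already absorbs much of any stable trait, as column C shows. The section is visibly unfinished: the moderator list is a placeholder, and the method reference and results table are still to be confirmed. Mediation is deferred to a later paper, runs only for mediators with a significant arm effect, and the SAP says the protocol will be consulted.

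These points rule out several stronger readings that a reader might infer:

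- That the SAP drops all measured confounders. It keeps baseline fatigue, baseline mediator, diagnosis and depressive symptoms.
- That the sponsor has withdrawn the protocol's safeguards. The SAP is silent on them.
- That any reported mediation would be nothing but confounding. The size depends wholly on correlations that the documents do not give.
- That measurement error adds false mediation. In these calculations it shrinks a true effect.
- That only one mediator measurement is used. The models contain a baseline and a follow-up value; the follow-up time is simply not stated.

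The objection does not dispose of the point. Protocol 10.2 makes the SAP govern all analyses, and SAP 11.3 states explicit models. An analyst who follows them will omit the two methods, and moving the results to a later paper does not change the model. More baseline covariates would also not fully remove causes that act after baseline, which is the reason to keep the sensitivity analysis.

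**Conclusion.** The point holds in limited form. SAP 11.3 narrows the protocol's covariate adjustment to four baseline items and leaves out both its measurement-error handling and its sensitivity analysis for unmeasured confounding, while keeping the causal label and the proportion mediated.

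The direction of each bias is clear: residual confounding can create an indirect effect, and mediator error tends to shrink one. The size cannot be fixed from the documents. For assumed confounder effects of 0.2 to 0.5 SD, the false proportion is about 1-5% for a stable trait when repeated measures correlate at 0.7 (up to 7% at 0.6 and 9% at 0.5). For causes acting after baseline it runs from about 6% to 28-39%. The larger figures should not be attached to baseline traits such as age or disease duration. Only the secondary mediation objective is affected; the primary intention-to-treat comparisons at 56 weeks are not.

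**What to change.** In SAP 11.3:

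1. Add one pre-specified set of collected baseline confounders to both the mediator and the outcome model. Candidates are age, sex, disease duration, self-reported disease activity, CRP, pain, sleep, continuous HADS and fibromyalgia. Because Protocol 3.3 allows outcome measures to act as mediators, leave out any variable that is itself the mediator under study, except as its own baseline value.
2. Restore the protocol's repeated-measures model for mediator measurement error.
3. Report the protocol's instrumental-variable sensitivity analysis beside every indirect effect and proportion mediated. If either protocol method is to be dropped, record the reason.
4. State the follow-up time point at which each mediator is taken.
5. Use baseline FSS in the outcome model when FSS is the outcome.

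No new data are needed. The cost is SAP wording, analyst time and possibly slightly wider intervals for the indirect effects.
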